1 STATEMENT OF COMPLIANCE

The REduCing Immunogenicity to PegloticasE (RECIPE) trial will be conducted in accordance with the International Conference on Harmonization Good Clinical Practice (ICH GCP), applicable United States (US) Code of Federal Regulations (CFR), and National Institute of Arthritis and Musculoskeletal and Skin Diseases (NIAMS) Terms and Conditions of Award. The Principal Investigator ([name], MSc) will ensure that no deviation from, or changes to the protocol will take place without prior agreement from the NIAMS, and documented approval from the Institutional Review Board (IRB), except where necessary to eliminate an immediate hazard(s) to the trial participants. All personnel involved in the conduct of this study have completed Human Subjects Protection and ICH GCP Training.

The protocol, informed consent form(s), recruitment materials, and all participant materials have been submitted and approved by the University of Alabama at Birmingham (UAB) Institutional Review Board (IRB) and vetted with the Food and Drug Administration (FDA) per the investigation new drug (IND) review. Any amendment to the currently approved protocol will require review and approval by the IRB before the changes are implemented to the study. All changes to the consent form will be IRB approved; in be obtained from any participants who provided consent, using a previously approved consent form.

2 PROTOCOL SUMMARY

2.1 SYNOPSIS

Title: Reducing Immunogenicity to Pegloticase (RECIPE)

Study Description: Pegloticase treatment for chronic refractory gout is limited by

immunogenicity. The investigators propose the REduCing Immunogenicity to PegloticasE (RECIPE) trial to investigate the question of whether a short course of immune modulating therapy with mycophenolate mofetil (MMF) can significantly and safely attenuate immunogenicity to pegloticase and ensure patients afflicted with chronic refractory gout have better

treatment outcomes and improved quality of life.

Objectives: Evaluate feasibility and preliminary efficacy and safety of a short course of

immunosuppressive therapy to prevent immunogenicity conferred by

pegloticase.

Endpoints: Primary Endpoints: The co-primary aims of our proof-of-concept double-

blind study are to first assess the feasibility and preliminary efficacy of a short course of immune modulating therapy with daily mycophenolate mofetil (MMF). We will explore the future full-scale study hypothesis that administering MMF for 12 weeks can safely attenuate immunogenicity conferred by pegloticase as determined by the proportion of participants achieving and maintaining a serum urate (sUA) \leq to 6 mg/dL for 12 weeks, compared to concurrent controls. After 12 weeks of co-administration of

MMF with pegloticase or placebo, all participants will continue on

modulation after discontinuation of the short course of MMF by: a)

pegloticase for an additional 12 weeks without combination MMF therapy to evaluate the longer-term benefits and safety of this approach. The second co-primary safety aim will assess the incidence and types of adverse events/infusion reactions potentially associated with MMF. Secondary Endpoints: 1) Determine the 6 month durability of immune

assessing the absolute change in serum urate from baseline to Week 24, and Week 12 to Week 24, and b) determining the proportion of participants with serum urate ≤ 6 mg/dL through 24 weeks, and Week 12 to Week 24; 2) Identify and characterize the pegloticase immune response by immunoglobulin isotypes (IgG and IgM), specificities, and antibody titer, and 3) Examine patient reported outcomes (PROs) using the National institute of Health (NIH) supported Patient Reported Outcomes Measurement Information System (PROMIS) and Gout Impact Scale (GIS)

instruments.

Study Population: We will enroll 32 adults (≥ 18 years of age) diagnosed with chronic

refractory gout, defined as persons whose signs and symptoms are inadequately controlled with urate lowering therapy (e.g. xanthine oxidase

inhibitors or uricosuric agents) at a medically appropriate dose or for whom these drugs are contraindicated. Recruitment will include men and

women of all races/ethnicities.

Phase: Phase II Trial

Description of University

Sites/Facilities Enrolling

Participants:

University of Alabama at Birmingham (Study Clinical Coordinating Center

and Data Coordinating Center); University of Michigan.

Description of Study Intervention:

Phase II, double blind, placebo controlled multisite proof-of-concept trial in participants initiating pegloticase for treatment of chronic refractory gout. Participants will be randomized (3:1) to one of two study arms, a pegloticase + MMF or a pegloticase + placebo study arm study arm.

Experimental: pegloticase + MMF

Participants randomized to this arm will receive pegloticase + MMF

Placebo Comparator: pegloticase + placebo (PBO)

Participants randomized to this arm will receive pegloticase + placebo

Study Duration: 24 months

Participant Duration: Up to six months (24 weeks)

2.2 SCHEMA

Figure 1. RECIPE Study Patient Level Timeline

Pegloticase + PBO (2g)
(n = 8)

Pegloticase only (n = 32)

In the second of the second

2.3 TABLE 1. SCHEDULE OF ACTIVITIES (SOA)

	Screen/	'Run-In					Phase 1	L .				Phase 2			Phase 3					
	V1	V2	V3	V4		V6				V10	V11		V13		V15	V16	V17	V18	V19	V20
	(-4	(-2	(0	(1	V5	(3	V7 (4	V8	V9	(10	(12	V12	(16	V14	(20	(22	(24	(28	(32	(EOS/ET)
Study procedures	wks)	wks)	wks)	wks)	(2wks)	wks)	wks)	(6wks)	(8 wks)	wks)	wks)	(14wks)	wks)	(18wks)	wks)	wks)	wks)	wks)	wks)	(36 wks)
ICF	X																			
Medical history	X										.,									
Physical exam	X	.,	.,		.,		.,	.,	,,	.,	X	,,	.,		.,	.,	X			
Vital signs* PROS	X	Х	X		Х		X	Х	X	Х	X	Х	X	Х	X	Х	X			
Assess flares,	^		^				^		^		^		^		^		^			
Update med conditions and meds		Х	Х		Х		х	Х	Х	Х	х	х	х	Х	Х	Х	Х			
Assess AEs ^ℓ			Х		Х		Х	Х	Х	Х	Х	Х	Х	Х	Х	Х	Х	Х	Х	Х
Dispense MMF/PBO		X (500 mg/ 2x per day)- week 1 and X (1 g/ 2x per day)	X [¥] (1 g/2x per day)		X (1 g/ 2x per day)		X (1 g/ 2x per day)	X (1 g/ 2x per day)	X (1g/2x per day)	X (1 g/ 2x per day)										
Pill count			Х		Х		Х	Х	Х	Х	Х									
Targeted PE/joint assess			х		Х		Х	Х	х	х		Х	х	Х	х	х				
CBC with diff	Х		Х	Х	Х	Х	Х	Х	Х	Х	Х	Х	Х	Х	Х	Х	Х			
HIV1 and 2 Antibody Screen	Х																			
IgG	Х		Х					Х			Х									
sUA (Pre Infusion Weeks 0-24 ⁺⁺)	х	Х	х	х	х		Х	х	х	х	х	х	х	х	х	х	х			
Pregnancy testing	X (serum)	х	х		х		х	Х	х	х	х	Х	х	х	х	х	х			
CMP	X	Х	Х		Х		Х	Х	Х	Х	Х	Х	Х	Х	Х	Х	Х			
G6PD	Х		_			_														
Peg Ab/Mechanistic collection/ storage ^f	Х		Х					Х			Х			х			Х	Х	Х	Х
MMF Adherence			Х	Χ	Χ	Х	Χ	Х	Х	Х	Х									
Gout flare prophylaxis [‡]		х	Х		Х		Х	Х	Х	Х	Х	Х	Х	х	Х	Х				
Administer pegloticase≠	Dland Count with		Х		х		Х	х	Х	Х	Х	Х	Х	Х	Х	Х				

3 INTRODUCTION

3.1 STUDY RATIONALE

Pegloticase, a recombinant modified mammalian urate oxidase (uricase), that is approved by the Food and Drug Administration (FDA) and the European Commission for use in gout patients is very efficacious in reducing serum urate (**Figure 2**) and improving clinical signs and symptoms of gout, such as tophi size (**Figure 3**). However, pegloticase has been associated with a high rate of infusion reactions (IRs) including anaphylaxis.

[figure not shown]
The ability of pegloticase to induce antibody production (leading to the need to stop therapy) raised the possibility that by reducing anti-pegloticase antibodies via an immune modifying drug, the loss of response to the drug could be prevented or delayed, as proposed in this study.⁶

3.2 BACKGROUND

Gout affects approximately 4% of the U.S. population, is the most common form of inflammatory arthritis in men, and is associated with decreased quality of life. The frequency of gout is increasing worldwide, with prevalence rates

estimated to be as high as 7% in older men, based on our work and the work of others. 10-12 It is estimated that up to 400,000 (up to 5% of the estimated 8 million persons with gout) in the United States experience chronic refractory gout, characterized by ongoing symptoms of active disease and a failure to control/maintain serum urate < 6 mg/dL with conventional xanthine oxidase inhibitors (i.e. allopurinol and febuxostat) and uricosuric agents (i.e. probenecid). 2,13-15 These patients often have significant, disabling urate deposits in soft tissues and bone known as tophi.

Figure 2. Urate reducing efficacy of pegloticase ¹

As stated in the study rationale (section 2.1), pegloticase has been associated with a high rate of infusion reactions (IRs) including anaphylaxis. IRs occurred in 26% of participants on pegloticase compared to 5% in placebo, and anaphylaxis

was reported in 5% of participants on pegloticase vs. 0% on placebo.⁵ Additionally, in one study the drug's immunogenicity leads to antipegloticase antibody (Ab) formation and associated loss of efficacy manifested by a rapid increase in serum urate levels in roughly 42% of all participants (n=212).^{5,16}

A relationship between the loss of urate-lowering efficacy (indicated by a rise in serum urate levels) and high-titer antibody formation was initially identified in a post-hoc analysis of two studies. ^{1,5} Participants with high anti-pegloticase antibody titers (>1:2430) experienced a significant loss of pegloticase activity that was attributed to more rapid clearance of drug in the presence of these antibodies. Sixty-nine (41%) of 169 patients receiving pegloticase developed high titer anti-pegloticase antibodies and

Figure 3. Hand tophi and sequential response to pegloticase ^{2,3}

subsequently lost response to the drug.¹⁷ In a second study, only 1 of 52 participants with high antibody titers maintained a response to pegloticase (serum urate < 6.0 mg/dL).⁵ In addition, 60% participants with high titers developed IR.^{5,18} Anti-pegloticase antibodies were largely directed to the polyethylene glycol (PEG) portion of the molecule and altered the pharmacokinetic clearance of pegloticase, resulting in inhibition of serum urate lowering activity.¹⁷

The ability of pegloticase to induce Ab production (leading to the need to stop therapy) raised the possibility that by reducing anti-pegloticase antibodies via an immune modifying drug the loss of response to the drug could be prevented or delayed, as proposed in this study. The rationale for use of mycophenolate moefitil as an immunomodulatory agent to attenuate pegloticase immunogenicity is discussed in section 4.2.2.

3.3 RISK/BENEFIT ASSESSMENT

3.3.1 KNOWN POTENTIAL RISKS

The known risks for participants as a result of participation in the RECIPE study are summarized below. This includes risks associated with the proposed study medications as well physical, psychological, social, economic, and/or legal risks from participating in this study.

- 1. Participants may experience pain from the needle used during phlebotomy, as well as possible bruising and soreness at the phlebotomy site. Pain following injection and bruising will subside over time.
- 2. Participants may experience some anxiety in completing questionnaires about their gout. The questionnaires should take <20 minutes to complete. Anxiety following completion of the questionnaires should subside over time.
- 3. Immediate and longer-term drug specific risks for all study drugs All study drugs to be tested/administered in the RECIPE study are FDA approved for use in various conditions. Risk associated with each are listed below and taken from package inserts and published literature (see Appendices 4, 5, and 6):

a. Mycophenolate Mofetil (MMF) (Oral ingestion).

i. Immediate Risks

- Nausea—20%; often subsides over time and following discontinuation of MMF
- Persistent diarrhea—36%; Subsides over time and following discontinuation of MMF
- Gastrointestinal bleeding requiring hospitalization—1.7%-5.4%
- o Neutropenia—2-3.6%; Subsides over time following discontinuation of MMF
- Decreased immune function and corresponding increased susceptibility to bacterial, viral, fungal, and protozoal infections, including opportunistic infections—1%-10%
- Other symptoms, occurring at rates of 1% to 10%, include hypertension, hypotension, tachycardia, chills, pain, musculoskeletal discomfort, and rash/acne

ii. Longer Range Risks

- Mycophenolate mofetil may increase the risk of developing lymphoma (a type of cancer of white blood cells) and other malignancies, particularly of the skin—1%-10%. Participants will be monitored for safety including malignancies during the study. To reduce the chances of skin cancer, participants will be encouraged to wear protective clothing and using an effective sunscreen when exposed to sunlight.
- o In rare cases in conditions (e.g. transplant, Systemic Lupus Erythematosus (SLE)) other than gout mycophenolate mofetil has been linked (incidence rate of 14.4 cases/100,000 person-years and 289/100,000 person-years respectfully) with a serious disorder of the brain known as Progressive Multifocal Leukoencephalopathy (PML). Following discontinuation of MMF patient conditions typically improve with marked reduction of weakness, and in follow-up MRI showed regression of lesions over the next 6 months. We will actively monitor participants and in the event of suspected diagnosis of PML, MMF will be withdrawn.
- Mycophenolate mofetil use is associated with increased risks of pregnancy loss and congenital malformations.

b. Pegloticase (Infusion)

i. Immediate Risks

It is common for potent urate lowering therapies to lead to acute attacks of gout. Other uncommon symptoms reported in at least 5% patients treated with pegloticase that may occur during the study period are ecchymoses, sore throat, constipation, chest pain, and vomiting. Serious allergic reactions may happen in some people while receiving infusion of pegloticase. These infusion reactions can be serious and usually happen within 2 hours of the infusion. Chest discomfort (15%), flushing (12%), and dyspnea (11%) are the most common symptoms. Symptoms associated with pegloticase infusion resolve with slowing, interrupting, or stopping the infusion. 91% of these symptoms occur in patients with serum urate concentrations greater than 6 mg/dL. Therefore, all participants serum urate will be checked prior to infusion and any participant with 2 or more serum urate test > 6 mg/dL (following initial infusion) will not be infused and will be removed from the study. Symptoms associated with infusion reactions include:

- Hemolysis; Individuals with G6PD deficiency are excluded from the study
- O Join pain 14%; Pain following injection. Pain subsides over time
- o Difficulty breathing 14%; Subsides over time
- Muscle spasms 14%; Subsides over time
- o Nausea 9%; Subsides over time
- Fever 14%; Subsides over time
- Back pain 14%; Subsides over time
- Diarrhea 14%; Subsides over time
- Erythema 14%; Subsides over time
- Hypersensitivity 14%; Subsides over time
- Rash 29%; Subsides over time
- Pain/bruising at the infusion site; Pain following injection and bruising will subside over time.
- Gout flares also known as gout attacks; Participants will be placed on a NSAID and/or colchicine regimen to help manage pain/discomfort. Flare/attack will subside over time
- Other symptoms, occurring at rates of 2% to 5%, included dizziness (5%), vomiting (5%), pain (4%), chills (3%), hypertension (3%), hypotension (3%), tachycardia (3%), feeling hot (2%), musculoskeletal discomfort (2%), and wheezing (2%)
- Participants will be observed for any signs of a serious allergic reaction during and after the treatment with pegloticase for infusion reactions
- Pegloticase has not been formally studied in patients with congestive heart failure, but some patients in clinical trials have experienced exacerbation. Patients who have diagnosed congestive heart failure will not be enrolled in the study

ii. Longer Range Risks

The risks to pregnant women or an unborn baby when taking pegloticase is not fully known.

c. Colchicine (Oral Ingestion for flare prophylaxis)

i. Immediate Risks

- The most commonly reported side effects for the prophylaxis of gout with colchicine was diarrhea (23%) and sore throat pain (1%-10%). These symptoms subside over time following discontinuation of colchicine.
- o In rare case (1-10%) more serious gastrointestinal bleeding may occur. Participant's with known gastrointestinal problems, such as a peptic ulcer or colitis, will be advised to consult with study doctor and their doctor before taking colchicine.
- All participants will be instructed not to ingest/drink grapefruit and Seville oranges or to drink grapefruit juice or Seville orange juice.

ii. Long Range Risks

 Colchicine has been associated in animal reproduction studies as having an adverse effect on the fetus, however there are no adequate and well-controlled studies in humans.

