6.2 EXCLUSION CRITERIA

- Weight > 160kg (352.74 lbs.)
- Any serious acute bacterial infection (2 weeks prior to Visit 1), unless treated and complete resolved with antibiotics
- Severe chronic or recurrent bacterial infections (such as recurrent pneumonia, chronic bronchiectasis)
- Current immunocompromised condition, including current or chronic treatment with immunosuppressive agents (prednisone or equivalent dose > 5 mg/day)

- Participants at risk for tuberculosis (TB). Specifically, participants with: i) current clinical, radiographic or laboratory evidence of active or latent TB; ii) a history of active TB within the last 3 years even if it was treated; iii) a history of active TB greater than 3 years ago unless there is documentation that the prior anti-TB treatment was appropriate in duration and type
- Known history of Hepatitis B surface antigen-positive or Hepatitis B DNA positive participants.
- Known history of Hepatitis C RNA-positive participants
- Human Immunodeficiency Virus (HIV) infection positive
- G6PD deficiency (tested at Screening/Visit 1)
- Severe chronic renal impairment (glomerular filtration rate [GFR] <25 mL/min/1.73 m2) or currently on dialysis
- Participants having any transplant surgery requiring maintenance immunosuppressive therapy
- Non-compensated congestive heart failure, uncontrolled arrhythmia, treatment for acute coronary syndrome (myocardial infarction or unstable angina), or hospitalization for congestive heart failure within 3 months of screening or uncontrolled blood pressure (>160/100 mm Hg) at baseline (Screening/Visit 1 and Week 0/Visit 3)
- Pregnant, planning to become pregnant, breast-feeding, or not on an effective form of birth control (defined in Section 8.3.8.2, see MOOP Section 2.f.2 Informed Consent)
- Prior treatment with pegloticase, another recombinant uricase, or concomitant therapy with a polyethylene glycol (PEG)-conjugated drug
- Known allergy to pegylated products or history of anaphylactic reaction to a recombinant protein or porcine product
- MMF treatment is contraindicated or considered inappropriate
- Recipient of an investigational drug within 4 weeks prior to study drug administration or plans to take an investigational agent during the study
- Current liver disease as determined by alanine transaminase ALT or aspartate transaminase (AST) levels >3 times upper limit of normal
- Currently receiving treatment for ongoing cancer, excluding non-melanoma skin cancer

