6.5 STRATEGIES FOR RECRUITMENT AND RETENTION

Participant Recruitment

We will recruit and enroll 32 adults (≥ 18 years of age) whose signs and symptoms are inadequately controlled with urate lowering therapy (e.g. xanthine oxidase inhibitors or uricosuric agents) at a medically appropriate dose or for whom these drugs are contraindicated. Recruitment will include men and women of all races/ethnicities. Recruitment will occur at UAB and UM. Patients will also be recruited directly from the UAB/UM hospitals and outpatient care facilities (e.g. UAB/UM Rheumatology Clinics each seeing greater than 1000 gout patients per year). Advertisements will be placed in the web page www.researchmatch.org, Birmingham/Ann Arbor metro area local newspapers, and UAB/UM campus publications. The inclusion and exclusion criteria will be reviewed with all potential participants, and informed consent will be obtained by the principal investigator, one of the co-investigators, or a trained member of the study staff. Study procedures will not begin until signed informed consent has been obtained.

The study investigators and staff will have meetings bi-weekly to monitor site recruitment and to determine any intervention for poor recruitment. In the event a problem is identified by either study site PI or staff, a teleconference/webinar will be scheduled to review the issue. These teleconferences/webinars will include discussions of overall recruitment status and identified barriers to recruitment experienced by the site with the study team

Participant Retention

During the screening and enrollment process, contact will be made with participants in a variety of ways (letters, staff contact by phone and in person) for optimal retention. To increase retention, we hire engaging, attentive, and responsive staff and who work with patients to provide flexible apt times where needed. The following major principals and commonly used strategies to maximize retention and minimize loss to follow-up will be employed during the trial:

- Stressing the idea that participants have an active role in the research and are part of the research team
- Enhancing participant's understanding of the study's mission and the protocol
- Stressing that retention efforts begin with recruitment and are an ongoing process
- Building participant relations and participant satisfaction, with the study staff taking a central role on this effort

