8.2 PARTICIPANT DISCONTINUATION/WITHDRAWAL FROM THE STUDY

Participants are free to withdraw from participation in the study at any time upon request.

An investigator may discontinue or withdraw a participant from the study for the following reasons:

- Pregnancy
- Significant study intervention non-compliance
- If any clinical adverse event (AE), laboratory abnormality, or other medical condition or situation occurs such that continued participation in the study would not be in the best interest of the participant
- Disease progression which requires discontinuation of the study intervention
- If the participant meets an exclusion criterion (either newly developed or not previously recognized) that precludes further study participation
- Participant unable to receive study intervention for 1 infusion period

The reason for participant discontinuation or withdrawal from the study will be recorded on the Study Closeout/Withdrawl/Termination CRF. Participants who sign the informed consent form and are randomized but do not receive the study intervention may be replaced.

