9 STUDY ASSESSMENTS AND PROCEDURES

This study will be coordinated by the University of Alabama at Birmingham (UAB). All study visits and procedures will be performed at the United States, at UAB, the University of Michigan, and up to 6 to be named sites. Enrollment will be competitive between sites. Frequency of study visits and clinical evaluations can be found in **Table 1**. Following the first 12 week dual therapy phase, participants will be given an additional three months of open-label pegloticase only therapy (see **Figure 1**) and will be followed to better understand the long-term efficacy (durability) of this approach, which is essential for future studies. Specifically, we will whether assess the durability of the short course of MMF continues over the next 12 weeks in the absence of MMF.

Participants will be seen according to schedule of visits and evaluations outlined in **Table 1** and per the details that follow:

Visit 1 - Screening Visit

The screening visit will take approximately 1 hour to complete. Potential participants will be screened to determine if they satisfy all inclusion and exclusion criteria. Men and women 18 years of age or older will be invited to proceed with informed consent (IC) and enroll in the study. At the screening visit, the study objectives will be explained to potential participants. After all questions raised by a potential participant are answered, and before any protocol-specified screening procedures are initiated, they will be offered the IC for the screening evaluation. A copy of the signed and dated IC form must be provided to the participant. After IC is obtained, a participant number will be assigned. All screening procedures must be completed and eligibility criteria met prior to start of immune-modulating therapy and pegloticase infusions. Basic demographic information and reason(s) for exclusion must be completed on the specified case report form (eCRF) pages for all participants who signed an ICF, but never received pegloticase. During the screening visit, the following procedures will be performed, and information will be obtained to determine eligibility to continue in this research study:

- o Review inclusion/exclusion criteria
- o ICF
- o Date of birth
- Self-reported race/ethnicity
- Medical history that might preclude study participation
- Gout history and symptom severity
- Medication review

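### Section 3.3.1 says patients with diagnosed congestive heart failure are not enrolled, but the 6.2 exclusion list does not bar compensated cases without a recent admission

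*Combined protocol and SAP*

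**What the plan says.** Section 3.3.1, in the list of immediate pegloticase risks, gives the background: "Pegloticase has not been formally studied in patients with congestive heart failure, but some patients in clinical trials have experienced exacerbation". The next sentence in the same bullet states the consequence for enrolment: "Patients who have diagnosed congestive heart failure will not be enrolled in the study". It is not limited by severity, compensation or time since the last episode.

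Section 6.2 deals with heart failure inside one longer cardiovascular criterion. It opens with "Non-compensated congestive heart failure, uncontrolled arrhythmia, treatment for acute coronary syndrome" and goes on to "hospitalization for congestive heart failure within 3 months of screening", before turning to uncontrolled blood pressure.

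The criteria in section 6 are the ones sites work from. Under 6.5, "The inclusion and exclusion criteria will be reviewed with all potential participants". For Visit 1, section 9 says: "Potential participants will be screened to determine if they satisfy all inclusion and exclusion criteria".

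**The concern.** The two sections give different answers for one kind of patient: someone with a heart-failure diagnosis who is compensated and has not been admitted recently. Section 3.3.1 says this patient is not enrolled. The heart-failure criterion in 6.2 lets the patient through.

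The 3.3.1 sentence is a safety statement, and the protocol supplies its own reason for it. If sites screen from 6.2, as section 9 tells them to, they can enrol someone the protocol says is not in the trial. Exposure is repeated: section 5.1 plans up to 12 infusions, and section 7.1.2 gives each in 250 mL of sodium chloride, with up to 500 mL allowed after an infusion reaction. Whether that is acceptable in compensated heart failure is a clinical question, and the protocol should answer it once.

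There is a practical side as well. Section 5.1 foresees two named sites and up to 6 more. Section 11.1.10 treats any noncompliance with the protocol as a deviation and asks for a report within 48 hours if safety is affected. As the text stands, a site and a monitor could disagree on whether enrolling such a patient is a deviation.

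**Working it through.** No arithmetic applies. The check sets the two eligibility statements side by side, patient type by patient type, and looks for anything else in the document that would settle the matter.

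| Patient | Section 3.3.1 | Heart-failure criterion in 6.2 |
|---|---|---|
| Heart failure, not compensated | Not enrolled | Excluded |
| Heart failure with an admission for it in the 3 months before screening | Not enrolled | Excluded |
| Diagnosed, compensated heart failure, no such admission | Not enrolled | Not excluded |

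The sections agree on the first two rows and disagree on the third. The punctuation of the 6.2 criterion leaves some doubt about how much of the sentence the 3-month window covers, but on either reading the third row is the same.

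*Other routes in 6.2.* The remaining route is the last criterion, which excludes a person the investigator considers a poor candidate because of undue risk or likely non-compliance. It gives cognitive impairment as its example and does not name heart failure.

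*Other mentions of heart failure.* In the supplied text, heart failure appears only in these two places. No sentence says whether 3.3.1 or 6.2 takes precedence. The 11 entries in the amendment log (versions 2.0 to 12.0) do not mention it. That silence does not show which wording was intended, and the summary of changes for the current amendment was on a page not supplied.

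*Is 3.3.1 meant to be enforced through 6.2?* The same risk list says that people with G6PD deficiency are excluded, and 6.2 carries a matching criterion, tested at screening. An exclusion announced in this list would therefore be expected to reappear in 6.2. The heart-failure one reappears only in part.

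**The case against.** The strongest reply is that 6.2 is the formal eligibility list and 3.3.1 a summary of risks. The qualifiers in 6.2 look deliberate, and they would be redundant if every diagnosed case were barred. On that view 3.3.1 is a loose paraphrase and nothing is wrong with whom the trial enrols. This is a fair argument about intent, and it may be right. It does not remove the conflict: the 3.3.1 sentence is categorical and follows directly on a safety reason, and if 6.2 governs, that sentence is untrue as it stands.

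Other protections exist. Section 11.1.7 names medical monitors who answer investigators' questions about the protocol. Section 9.3.8.1 requires vital signs and a chest examination before each infusion, and section 7.1.2 about an hour of observation afterwards. These stand, but the monitors help only a site that notices the conflict, and the infusion checks do not replace an eligibility rule.

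Three stronger readings are tempting, and the documents do not support them:

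- A reader might infer that the protocol leaves compensated heart failure to site discretion. It does not say so. Applied literally, 6.2 gives one answer on heart-failure grounds: not excluded. Judgement enters only through the general investigator-opinion criterion.
- A reader might infer that detection at screening is optional. The Visit 1 list includes "Medical history that might preclude study participation" and a cardiovascular examination, and Table 1 schedules both history and examination. The diagnosis would probably be found; what is missing is one rule for what follows.
- A reader might extend the gap to withdrawal, because 8.2 lists this ground: "If the participant meets an exclusion criterion (either newly developed or not previously recognized) that precludes further study participation". But 8.2 is permissive and also covers any other medical condition that makes continuing against the participant's interest, so the mismatch leaves nobody whom an investigator could not withdraw.

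**Conclusion.** The inconsistency is real and lies in the current text. A patient with diagnosed, compensated heart failure and no admission in the 3 months before screening passes the 6.2 heart-failure criterion, although 3.3.1 says such patients are not enrolled. Only the investigator-opinion exclusion could keep the patient out.

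Its reach is narrow. The documents give no heart-failure prevalence, so the number affected cannot be determined and may be zero. It is worth correcting because a safeguard stated as fact is only partly enforced by the list that sites apply.

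The conclusion assumes that sites screen from section 6, as 6.5 and section 9 indicate, and that no document outside the supplied text resolves the point. The Manual of Operating Procedures, the appendices and the screening and consent forms were not available.

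**What to change.** Replace the two heart-failure elements of the 6.2 criterion with *any diagnosed congestive heart failure*, so that the stated safeguard is enforced. Keep the arrhythmia, acute coronary syndrome and blood-pressure elements. If the 3-month window was also meant to cover acute coronary syndrome, restate it there so that it is not lost with the admission clause. The downside is a slightly smaller eligible pool, by an amount the documents do not allow to be determined.

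If the sponsor intends compensated cases to be eligible, leave 6.2 alone and rewrite the 3.3.1 sentence to match it, so that the exacerbation risk described there is shown to apply to people who may be enrolled. This openly withdraws a stated safeguard. The choice is clinical and belongs to the sponsor.

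Either way, check that the screening and consent forms and the Manual of Operating Procedures use the same criterion. The cost is one line of text, the funder agreement and IRB approval that section 1 requires for a protocol change, and that check.
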